#### 6.4.5 Early patient discontinuation

#### 6.4.5.1 End of treatment

Patients may withdraw voluntarily from the study or be withdrawn, at the investigator's discretion, at any time. They may be considered as discontinued if they declare their intention to discontinue, or if they do not return for visits, or if they are lost to follow-up for any other reason. Patients may be withdrawn from the study by the investigator for any of the following reasons:

- Acute or progressive vision loss confirmed by a new evaluation of the visual field
- Increased tumor volume defined as tumor volume growth (>20%) and confirmed in a second MRI performed approximately one month later
- Pregnancy
- Adverse event(s)
- Uncontrolled diabetes mellitus
- Clinically significant abnormal laboratory value(s)
- Clinically significant abnormal result(s) of test procedures
- Protocol violation
- Lost to follow-up
- Administrative problems
- Death
- Patients who experience:
- ALT or AST > 3 x ULN and Total Bilirubin  $\ge 2$  x ULN and ALP < 2 x ULN
- ALT or AST > 5 x ULN and  $\le 8$  x persistent ULN for more than 2 weeks
- ALT or AST > 8 x ULN

If any of the discontinuation criteria is met, the study medication must be immediately discontinued. Additionally, appropriate safety follow-up monitoring must be performed, as defined on Section 7.5.2.3. Resuming the study medication after the discontinuation criteria are met is not allowed.

#### 6.4.5.2 Completion of the study evaluation

For patients considered as lost to follow-up (i.e., patients whose condition is not clear because they did not attend the study visits without declaring an intention to discontinue), the investigator must show "due diligence" by documenting the actions taken in the source-documents in order to contact the patient, such as, for example, dates of phone calls, registered letters, etc.

# 7 Visits and evaluations schedule

Tables 7-1 and 7-2 show a list of all evaluations for the Main Phase and the Extension Phase, respectively, and indicate with an "X" the visits to be performed. All data obtained from these evaluations must be confirmed in the patient's source-documentation. The table indicates which data are entered in the database (DB) or remain only on the source-documents (SD). The evaluations producing data for registration in the database and that are recorded in the eCRFs are listed using the eCRF name.

Table 7-1 Visits and evaluations schedule for the Main Study

					V401 E						10	11
Visit number	1	2	3	4	48	5	6	7	8	9	EOS 	Follow-up Visit 
Days 	Day -28 to -1	Day 0	Day 20	Day 28	Day 48	Day 56	Day 76	Day 84	Day 112	Day 140	Day 168	Day 196
Treatment week		Inclusion	Week 3	Week 4	Week 7	Week 8	Week 11	Week 12	Week 16	Week 20	Week 24	Week 28
	Screening 	Baseline/ Injection 1	Safety Only	Injection 2	Safety Only	Injection 3	Safety Only	Injection 4	Injection 5	Injection 6	(if the patient participates in the Extension Phase)	Safety Follow-up
Informed Consent Form (SD)	Х											
Demographics (DB)	Х											
Disease diagnosis and extent (DB)	Х											
Relevant medical history / current medical conditions (DB)	Х											
Evaluation of inclusion/exclusion criteria (SD)	Х											
Vital signs (DB)	Х	X	X	X	X	X	X	X	X	X	X	X
Physical examination (SD)	Х	Х	Х	Х	X	Х	Х	Х	Х	Х	Х	Х
Height (DB)	Х											
Weight (DB)	Х	Х	Х	Х	X	Х	Х	Х	Х	Х	X	Х
Evaluation of symptoms / Disease-related symptoms  (DB)	Х	Х	Х	Х	X	Х	Х	Х	Х	Х	Х	
ECOG Performance status (DB)	Х	Х	Χ	Х		Х	Х	Х	Х	Χ	X	Х
ECG (DB) 14	Х	Х	Х	Х		Х	Х	Х	Х	Х	X	
Blood pregnancy test 	Х							Х			Х	
Hematology (DB)	Х			Х		Х		Х	Х	Х	Х	

					V401 E						10	11
Visit number	1	2	3	4	48	5	6	7	8	9	EOS 	Follow-up Visit 
Days 	Day -28 to -1	Day 0	Day 20	Day 28	Day 48	Day 56	Day 76	Day 84	Day 112	Day 140	Day 168	Day 196
Treatment week		Inclusion	Week 3	Week 4	Week 7	Week 8	Week 11	Week 12	Week 16	Week 20	Week 24	Week 28
	Screening 	Baseline/ Injection 1	Safety Only	Injection 2	Safety Only	Injection 3	Safety Only	Injection 4	Injection 5	Injection 6	Injection 7# (if the patient participates in the Extension Phase)	Safety Follow-up
Coagulation parameter PT (D)	X	X	$X^{14}$	X 	X 	X 	X				X	
Coagulation parameter APTT (D)	X	X					X				X	
Urinalysis  (DB)	Х			Х		Х		Х	Х	Х	Х	
Fasting blood glucose, insulin 	X			X		X		X	X	X	X	
HbA1c 	х							Х			Х	
Chemistry  (DB)	Х			Х		Х		Х	Х	Х	Х	
LFTs (ALT, AST, total bilirubin, albumin, ALP, γ-GT) (D)	X	X	X 	X 	X 	X 	X				X	
HBs-Ag and anti-HCV (D)	X											
Vitamin B12, folic acid 	X										X	
Hormone evaluation  (DB)	Х			X				Х			Х	
Alpha subunit evaluation 	Х			Х				Χ			Х	
Visual field evaluation  (DB)	X	X 		X		X		Х	X	Х	X	
Gallbladder ultrasound (DB) 15	Х										Х	
Pituitary / Sella turcica MRI  Adverse events (DB)	X	X	X	X	X	X	X	X	X	X	X	

Page 61 Protocol No. CSOM230D2401

Page 62

Visit number	1	2	3	4	V401 E 48	5	6	7	8	9	10 EOS 	11 Follow-up
					40							Visit 
Days 	Day -28 to -1	Day 0	Day 20	Day 28	Day 48	Day 56	Day 76	Day 84	Day 112	Day 140	Day 168	Day 196
Treatment week		Inclusion	Week 3	Week 4	Week 7	Week 8	Week 11	Week 12	Week 16	Week 20	Week 24	Week 28
	Screening 	Baseline/ Injection 1		Injection 2	Safety Only	Injection 3	Safety Only	Injection 4	Injection 5	Injection 6	Injection 7# (if the patient participates in the Extension Phase)	Safety
Pasireotide LAR administration (DB)		X		X		X		X	Х	Х	X #	
Previous / concurrent medication  (DB)	Х	Х	X	Х	Х	Х	Х	Х	Х	Х	Х	
Study completion  (DB)												x 

# The pasireotide dose in this visit will be administered to selected patients, at the physician's discretion, if the patient is included in the Extension Phase, based on the response evaluated by the investigator to the benefit from the drug (Section 6.4).

- 1. A ± 3 day window will be allowed for scheduled visits and evaluations, unless otherwise indicated.
- 2. To be performed before administration of the study drug.
- 3. To be performed if the patient discontinues early or upon completion of the study.
- Disease-related symptoms to be evaluated: headache, visual disorders, fatigue, decreased libido, erectile dysfunction (only for men), irregular or interrupted menstrual cycles (only for non-menopausal women). The investigator will also ask patients to classify symptoms according to a 5-point scale (0 = absent, 1 = mild, 2 = moderate, 3 = severe, 4 = very severe). The remainder will be evaluated as absent or present.
- 5. A pregnancy blood test will be performed at the final follow-up visit, if a patient reports a delay in menstruation or according to the physician's opinion.
- Blood and urine must be collected before administration of the study drug. Patients must be fasting for 12 hours.
- 7. Hematology and coagulation include: hemoglobin, hematocrit (HCT), WBC count with differential, RBC count with differential, and platelet count; PT and APTT.
- 8. Complete chemistry includes: total cholesterol, low density lipoprotein (LDL) cholesterol, high density lipoprotein (HDL) cholesterol, triglycerides, calcium, phosphorus, chloride, sodium, potassium, inorganic phosphorus, creatinine, urea, uric acid, CPK, LDH, alkaline phosphatase,  $\gamma$ -GT, total protein, albumin, SGOT, SGPT, total bilirubin. If the total bilirubin concentration increases over 2.0 times the upper limit of normal, it must be differentiated in direct and indirect bilirubin at visits.
- Hormone evaluations (blood) pituitary disease evaluations: testosterone (for men), estradiol (for women), prolactin, free T4, TSH, LH, FSH, GH, IGF-I. cortisol. ACTH.

- 10. Evaluation by Standard Automated Perimetry (SAP). The Humphrey Field Analyzer is recommended. The window to perform the SAP must not be more than 7 days before the scheduled visit. If the visual field evaluation at Screening is performed no more than 14 days before Visit 2, it may be considered as baseline data and there is no need to repeat it for Visit 2.
- 11. Previous and concurrent medications comprise any therapy, including chemotherapy, radiation therapy, and surgery, or medication previously received, or ongoing treatment.
- 12. All medications / therapies used to treat tumor or symptoms in this study, given to a patient in a ≤ 4 week period after administration of the last dose of the study treatment, must be recorded in the eCRF. All patients will be followed up for safety for 56 days after administration of the last dose of the study drug.
- 13. Safety follow-up must be performed 56 ± 3 days after the patient has received the last pasireotide LAR dose. For patients who continue in the extension study, this visit will not be performed after the end of the main study, but 56 ± 3 days after the patient has completed the extension study.
- 14. The ECG will be performed before administration of the drug. On Visit 3 (Day 20) and on Visit 6 (Day 76), the ECG will be performed regardless of drug administration.

<del>15.</del> .

- 15. The window to perform gallbladder MRI and US [ultrasound] must not be more than 7 days prior to the scheduled visit.
- 16. If a patient is not assigned to the Extension Phase, the follow-up visit will be Visit 11.

Table 7-2 Visits and evaluations schedule for the Extension Study

Table 1-2 VISI	is and	Cvan	autio	113 30	)110u	u	JI (111	LAL	CHOI	J O	uuy										
Visit	10 	11	12	402	13	14	15	16	17	18	19	20	21	22	23	24	25	26	27	28	29
																				EOS	Follow-up 9
Week	24	28	32	35	36	40	44	48	52	56	60	64	68	72	76	80	84	88	92	96	Last dose + 8
																					weeks
Day	168	196	224	244	252	280	308	336	364	392	420	448	476	504	532	560	588	616	644	672	700
Injection	7	8	9		10	11	12	13	14	15	16	17	18	19	20	21	22	23	24		
Adverse events (DB)	Х	Х	Х	Х	Х	Х	Х	Х	Х	Х	Х	Х	Х	Х	Х	Х	Х	Х	Х	Х	X
Current medical	Х				Х			Х			Х			х			Х			Х	х
conditions (DB)					^			^			^			^			^			^	
Vital signs (DB)	Χ				X			Х			Х			Х			Х			Х	Х
Physical examination (SD)	Х				X			Х			X			Х			Х			Х	Х
Weight (DB)	Х				Х			Х			Х			Х			Х			Х	Х
Pituitary / Sella turcica	Х							Х						х						Х	
MRI								^													
Alpha subunit 	Х							Х						Х						Х	
ECG (DB)	Х				Х			X			Х			X			Х			X	
Gallbladder ultrasound	Х							Х												x	
(DB)	^							^												_ ^	
ECOG Performance status	X				Х			Х			Х			Х			Х			Х	х
(DB)	^				^			^			^			^			^			_ ^	^
Evaluation of symptoms /																					
Disease-related	Х				Х			Х			Х			X			Х			X	
symptoms (DB)																					
Blood pregnancy test 	Х							Х						X						Х	
Hematology (DB)	X							X						Х						Х	
Coagulation parameter PT	ΧE	хĸ	XK		XK	XK				Х	Х	Х	Х	Х		Х	Х	х	x	x	X
(D)	/\-	71.1	71.1	Χ	71.1	7111									X			~		_^_	^
Coagulation parameter	ΧE					Х				Х	Х	Х	Х	Х		Х	Х	х	х	x	
APTT (D)															X			~			
Urinalysis  (DB)	Х							Х						Х						Х	
Fasting blood glucose	Х							x						Ιx						x	
and insulin 2																					
HbA1c 	Х							Х						X						Х	
Chemistry 	Χ							Х						Х						Х	
LFTs (ALT, AST, total																					
bilirubin, albumin, ALP,	X			Х				Х						Х						Х	
γ-GT) (D)																					

Visit	10¹	11	12	402	13	14	15	16	17	18	19	20	21	22	23	24	25	26	27	28 EOS	29 Follow-up 
Week	24	28	32	35	36	40	44	48	52	56	60	64	68	72	76	80	84	88	92	96	Last dose + 8 weeks
Day	168	196	224	244	252	280	308	336	364	392	420	448	476	504	532	560	588	616	644	672	700
Injection	7	8	9		10	11	12	13	14	15	16	17	18	19	20	21	22	23	24		
Hormone evaluation  (DB)	Х							Х						Х						х	
Evaluation of the visual field 	Х							Х						Х						х	
Vitamin B12, folic acid 	Х							Х												Х	
Administration of Pasireotide LAR  (DB)	Х	Х	Х		Х	Х	Х	Х	Х	Х	Х	Х	Х	Х	Х	Х	Х	Х	Х		
Previous / concurrent medication  (DB)	Х	Х	Х	Х	Х	Х	Х	Х	Х	Х	Х	Х	Х	Х	Х	Х	Х	Х	Х		
Completion of the study  (DB)																					x

<sup>1 Patients who, according to the opinion of the physician in charge, are deriving benefit from pasireotide LAR treatment will be invited to participate in the extension phase.

<sup>2 Blood and urine must be collected before administration of the study drug. Patients must be fasting for 12 hours.

<sup>3 Hematology and coagulation include: hemoglobin, hematocrit (HCT), WBC count with differential, RBC count with differential, platelet count, PT, and APTT.

<sup>4 Complete chemistry includes: total bilirubin, total cholesterol, LDL, HDL, triglycerides, creatinine, urea, uric acid,  $\gamma$ -GT, total protein, albumin, SGOT, SGPT, CPK, LDH, alkaline phosphatase, sodium, potassium, inorganic phosphorus, chloride, and calcium. If total bilirubin concentration increases over 2.0 times the upper limit of normal, total bilirubin must be differentiated in direct and indirect reagent bilirubin.

<sup>5 Hormone evaluation (blood) — evaluations of pituitary disease: testosterone (for men), estradiol (for women), prolactin, free T4, TSH, LH, FSH, GH, IGF-I, cortisol, ACTH.

<sup>6 Evaluation by Standard Automated Perimetry (SAP). The use of the Humphrey Field Analyzer is recommended. The window to perform the SAP must not exceed 7 days before the scheduled visit.

<sup>7 Patients will continue to receive pasireotide LAR IM every 28 (± 3) days. Administration of the drug will be performed by a healthcare professional at the site. Administration of the last dose occurs on Week 92 (Visit 27).

<sup>8 All medications / therapies used to treat the tumor and symptoms in this study, administered to a patient for 4 weeks or less after administration of the last dose of the study treatment, must be recorded in the eCRF. All patients will be followed up for safety for 56 ± 3 days after administration of the last dose of the study medication.

<sup>9 The safety follow-up visit (Visit 29) must be performed 56 ± 3 days after the patient has received the last dose of pasireotide LAR.

<sup>10 A blood pregnancy test will be performed at the final follow-up visit, if a patient reports delayed menstruation or according to the physician's opinion.

Page 66 Protocol No. CSOM230D2401

# 7.1 Information to be collected in case of screening failure

Patients who do not meet eligibility requirements on Visit 1 are considered as screening failures. If a patient cannot start treatment for any reason, this reason must be entered in the Screening Record eCRF, and the patient's demographics will be entered in the Demographics eCRF.

# 7.2 Demographics / other baseline patient characteristics

Patients' demographics and baseline characteristics will include the following: demographics, diagnosis and disease extent, relevant medical history / current medical conditions, previous / concurrent medication administered, physical examination, including vital signs, laboratory evaluations (including, but not limited to, fasting blood glucose and insulin), urinalysis, visual field and radiological evaluations, alpha subunit level, and \_\_\_\_\_\_\_\_, if applicable.

Evaluations performed to determine eligibility include gallbladder imaging, MRI, ECG, ECOG performance status, and pregnancy blood test. Other safety tests include AEs and SAEs, hematology and coagulation, and chemistry evaluations.

The data will be recorded in the applicable eCRFs.

#### 7.3 Treatments

The study medication administered during the study must be documented in the Dose Administration eCRF. Date and time of dose administration will be recorded in the Dose Administration Record. Compliance will be evaluated by the investigator and/or study staff on all visits. Records of study drug used, treatment administered, and intervals between visits will be kept throughout the study. Drug accountability will be registered by the field monitor during site visits and upon completion of the study.

All drugs, including over-the-counter drugs and previous therapies for the disease, taken before administration of the study drug and continuing throughout this study must be documented in the Previous / Concurrent Medication eCRF.

In the Main Phase, patients will receive the study drug on Visit 2 (Day 0) and then every 4 weeks ( $28 \pm 3$  days) thereafter, i.e., on Weeks 4, 8, 12, 16, 20. Patients who enter the Extension Phase will receive the study drug starting on Week 24, and then every 4 weeks ( $28 \pm 3$  days) thereafter, until Week 92.

All therapies administered to a patient within 4 weeks after administration of the last dose of the study medication must be documented in the Therapy Since Discontinuation eCRF.

# 7.4 Efficacy

Tumor volume, hormone response, and relevant disease-related symptoms will be evaluated, as previously described in this protocol.

### 7.4.1 Primary efficacy evaluation

Tumor volume will be evaluated by MRI with gadolinium contrast in the Screening Phase (and will be considered as baseline imaging), on Weeks 4, 12, and 24 in the Main Phase, and on Weeks 48, 72, and 96 in the Extension Phase (see Tables 7-1 and 7-2).

# 7.4.2 Secondary efficacy evaluations

Tumor volume will also be evaluated as described on Section 7.4.1. Time to response will also be obtained (i.e., time to reach tumor volume decrease  $\geq 20\%$ ).

Disease-related symptoms will be reported by patients and recorded by the medical staff, on all Main Phase visits and on visits 13 (week 36), 16 (week 48), 19 (week 60), 22 (week 72), 25 (week 84), and 28 (week 96) of the Extension Phase.

Disease-related symptoms to be evaluated: headache, visual disorders, fatigue, decreased libido. Only for men: erectile dysfunction. Only for non-menopausal women: irregular or interrupted menstrual cycles. The investigator will also ask patients to classify the symptoms above according to a 5-point scale (0 = absent, 1 = mild, 2 = moderate, 3 = severe, 4 = very severe). The remaider will be evaluated as absent or present.

Hormone profiles, including growth hormone (GH), insulin-like growth factor I (IGF-1), follicle-stimulating hormone (FSH), luteinizing hormone (LH), adrenocorticotropic hormone (ACTH), thyroid-stimulating hormone (TSH), prolactin (PRL), cortisol, free T4, and estradiol (for women) or testosterone (for men), will be evaluated in the Screening Period (and will be considered as baseline data) and on Weeks 4, 12, and 24 of the Main Phase. Evaluations in the Extension Phase will be performed on Weeks 48, 72, and 96.

Alpha subunit levels will be measured in the Screening Period (and will be considered as baseline data), on Weeks 4, 12, and 24 in the Main Phase, and on Weeks 48, 72, and 96 in the Extension Phase.

# 7.5 Safety

#### 7.5.1 Adverse events

An AE for the purposes of this protocol is the onset of (or worsening of) untoward (pre-existing) sign(s), symptom(s), or clinical condition(s) occurring after signature of the Informed Consent Form, even if the event is clearly considered not related to the study drug(s). Refer to Section 6 for specific protocol definitions of study drug and study treatment.

AEs will be evaluated according to the Common Terminology Criteria for Adverse Events (CTCAE) version 4.0. If there is no CTCAE classification for an adverse event, mild, moderate, severe, and potentially fatal severities **or** grades 1 to 4 will be used. CTCAE grade 5 (death) will not be used in this study; this information will be gathered in the End of Treatment or Survival Information eCRF. AE monitoring must continue for at least 4 weeks after administration of the last dose of the study treatment.

AEs occurring before the study treatment is started, and after the Informed Consent Form is signed, are recorded in the Medical History / Current Medical Conditions electronic Case Report Form.

Abnormal laboratory values or abnormal test results only constitute AEs if they lead to clinical signs or symptoms, are considered clinically significant, or require therapy (e.g., any hematological abnormality requiring transfusion or treatment with cytokines), and must be recorded in the Adverse Events eCRF according to associated signs, symptoms, or diagnoses. Additionally, single abnormal laboratory values that are considered clinically significant (for example, causing study discontinuation or constituting, themselves, a serious adverse event) must be recorded in the Adverse Events eCRF. SAEs occurring after the Informed Consent Form is signed are recorded in the Adverse Event eCRF.

The occurrence of AEs must be obtained by means of indirect questioning to the patient on every visit throughout the study. AEs may also be detected when voluntarily reported by the patient during or between visits or through physical examination, laboratory tests, or other evaluations. Whenever possible, each AE must be evaluated to determine:

- 1. Severity grade (CTCAE grade 1 4)
- 2. Relationship to pasireotide LAR (suspected / non-suspected)
- 3. Duration (onset and end dates or if ongoing at the final examination)
- 4. Action taken (no action taken; study drug dose adjusted / temporarily interrupted; study drug permanently discontinued due to this AE; concurrent medication administered; non-drug therapy administered; hospitalization / prolonged hospitalization)
- 5. If serious, a serious adverse event (SAE) is defined as an event that:

- Is fatal or potentially fatal
- Results in persistent or significant disability / incapacity
- Constitutes a congenital anomaly / birth defect
- Requires hospitalization or prolongation of ongoing hospitalization, unless the hospitalization is for:
  - Routine treatment or monitoring of the indication studied; not associated to any condition deterioration (specify what this includes)
  - Elective or pre-planned treatment to a pre-existing condition that is not related to the study indication and did not worsen since the consent form was signed
  - Emergency outpatient treatment for an event that does not meet any of the SAE definitions provided above and does not result in hospitalization
  - Social reasons and temporary care in the absence of any deterioration of the general patient condition
- Is clinically significant, i.e., defined as an event that puts the patient at risk or that might require medical or surgical intervention to prevent one of the results listed above

# Unlike routine safety evaluations, SAEs are continuously monitored and have special reporting requirements; See Section 8.1.

All AEs must be properly treated. This treatment may include changes in treatment with the study drug, including possible interruption or discontinuation, start or interruption of concurrent treatments, changes in the frequency or nature of evaluations, hospitalization, or any other clinically required intervention. Once an AE is detected, it must be followed up until its resolution, and an evaluation must be performed on every visit (or more frequently, if required) regarding any change in severity, its suspected relationship to the study drug(s), any interventions required to treat it, and its outcome.

The information on already known common side effects related to the investigational drug may be found in the Investigator's Brochure (IB) or will be notified between IB updates as Investigator Notifications (INs). This information will be included in the patient's informed consent form and must be discussed with the patient during the study, as required.

#### 7.5.2 Special Safety

#### 7.5.2.1 Changes in blood glucose

The principal investigator must instruct patients about signs and symptoms of hyperglycemia, and evaluate the risks of hyperglycemia in all patients. It is recommended to follow the guidelines established by international associations specialized in diabetes, such as the American Diabetes Association (ADA) and the European Association for the Study of Diabetes (EASD) (Nathan 2009).

Patients with history or recent diagnosis of fasting glucose impairment, glucose tolerability impairment, diabetes mellitus, or at risk of developing these conditions must monitor blood glucose by means of a fingerstick capillary glucose test twice a day (fasting and 2 hours post-prandial). It is recommended that patients be encouraged to keep a blood glucose diary for appropriate disease management throughout the study, as well as to show the data collected to the physician / diabetes expert for evaluation. The data will not be collected by the sponsor.

It is advised that any patient experiencing fasting plasma glucose > 130 mg/dL (7.2 mmol/L), or 2-hour post-prandial capillary glucose (PPG)  $\geq$  180 mg/dL (10 mmol/L) in two consecutive measurements with an interval of approximately 14 days and/or HbA1c > 7% be evaluated by an diabetes expert for proper treatment (Position statement ADA 2010). Additionally, these patients must be informed on diabetes control. The start or adjustment of anti-hyperglycemic treatment must be considered as soon as possible, at the discretion of the diabetes expert. Additionally, these patients must start blood glucose monitoring by fingerstick capillary glucose test twice a day (fasting and 2 hour post-prandial) if it has not yet been performed. It is recommended that patients be encouraged to keep a blood glucose diary for appropriate disease management throughout the study, as well as to show the data collected to the physician / diabetes expert for evaluation. The data will not be collected by the sponsor.

Patients developing symptoms of uncontrolled diabetes mellitus and/or blood glucose levels consistently above 275 mg/dL (15.5 mmol/L), in spite of appropriate therapeutic interventions, must be discontinued from the study, as well as those patients whose HbA1c percentage is  $\geq 10\%$ , in spite of appropriate therapeutic interventions.

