### Rationale for the amendment

This amendment was implemented to address the following items of the original study protocol:

- Extension of the duration of treatment from week 24 to week 96:
  - In order to allow further long term safety and efficacy evaluation of the treatment with pasireotide LAR, patients who have derived benefit from treatment with this medication, according to the evaluation of the physician in charge, will be offered a 72-week extension period (i.e., patients will be followed up until week 96 and will have another safety follow-up visit on week 100)
  - A scheme including extension treatment was added (figure 4-2), in addition to the test schedule for the extension portion of the study (table 7-2). Thus, the changes implemented by this amendment are expected to be clarified
  - The duration of response evaluation for patients considered responsive until week 24 and the percentage of patients remaining with stable disease have been added to the objectives, in order to evaluate the duration of study medication efficacy
- For consistency purposes, in the pasireotide clinical trials program (SOM230), patients with uncontrolled diabetes and/or blood glucose values consistently above 275 mg/dL instead of 200 mg/dL must be withdrawn from the study, regardless of appropriate therapeutic interventions and/or whether HbA1c value is = 10 % instead of higher than 8%
- Clarification on the procedure used for QTcF prolongations.
- Correction of discrepancies and typographical errors or addition of absent secondary information seen in the original protocol:
  - In order to be consistent with the study design, the term "randomization" has been replaced with "enrollment visit (Visit 2)", as there will be no randomization in this study, since it is single-armed
  - Changes to the protocol synopsis in order to maintain consistency with the protocol
- Clarification that only glucose and insulin will be evaluated, and not OGTT (oral glucose tolerance test)

• Clarification that the ECG and campimetry evaluations will be performed locally

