  - End of Study and safety visits timepoints added to  $28 \pm 3$  days and  $56 \pm 3$  days after the administration of the last dose of the study medication, respectively, for extension phase patients who discontinue treatment
- 7 Visits and evaluations schedule
  - On Table 7-1
    - The information that  $a \pm 3$  day window will be allowed for scheduled visits has been deleted.
    - Clarification on item 10 that if the visual field evaluation at Screening is performed no more than 14 days after Visit 2, it may be considered baseline data and there is no need to repeat it for Visit 2
    - Item 15 deleted: At the Screening Visit and Visit 10 (EOS), blood glucose and insulin will be measured at fasting at timepoint 0 during OGTT, and will be considered as baseline data for OGTT. Regarding this change, the glucose and insulin OGTT evaluation has also been deleted from the table
  - Added Table 7-2 Visits and evaluations schedule for the Extension Study with its specifications
- 7.3 Treatments
  - Replacement of the word responsibility with accountability
  - It has been clarified that Extension Phase patients will receive the medication starting on Week 24 and every 4 weeks  $(28 \pm 3 \text{ days})$  thereafter, until Week 92
- 7.4.1 Primary efficacy evaluation
  - Evaluation timepoints added on Weeks 48, 72, and 96 in the Extension Phase
- 7.4.2 Secondary efficacy evaluations
  - Visits 13, 16, 19, 22, 25, and 28 of the Extension Phase added for recording of disease-related symptoms
  - Clarification that symptoms not described in the section will be evaluated as absent or present
  - Weeks 48, 72, and 96 added for efficacy evaluation
- 7.5.2.1 Changes in blood glucose
  - 2008 ADA Position statement replaced by the 2010 statement
  - For consistency purposes, in the pasireotide clinical trials program (SOM230), blood glucose minimum levels have been changed from 200 to 275 mg/dL, as well as HbA1c percentage from 8 to 10%

- 7.5.2.2 Changes in QT interval
  - It has been clarified that if the ECG is abnormal at Visit 10 and no additional pasireotide LAR dose is administered, then the follow-up is at the investigator's discretion
  - It has been clarified that, on Scenario B of ECG change, the Holter ECG test must be recorded as soon as possible, within 7 days after the initial abnormal ECG, and not 30 minutes before dosing on the next pasireotide LAR administration day
  - Figure 7-1
    - Week 6 has been replaced with week 7 for QTcF evaluation

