Creatinine (mg/dL)				
N				
Mean				
Median Standard Deviation				
Minimum				
Maximum				
Normal				
Abnormal				
CS				
NCS				
Uric acid (mg/dL) N				
Mean				
Median				
Standard Deviation				
Minimum Maximum				
Waximum				
Normal				
Abnormal				
CS NCS				
CPK (U/L) N				
Mean				
Median				
Standard Deviation				
Minimum Maximum				
Normal				
Abnormal CS				
NCS				
104 (1/1)				
LDH (U/L) N				
Mean				
Median				
Standard Deviation Minimum				
Maximum				
Normal				
Abnormal				
CS				
NCS				

```
Total protein (mg/dL)
   Mean
   Median
   Standard Deviation
   Minimum
   Maximum
   Normal
   Abnormal
     CS
    NCS
Total cholesterol (mg/dL)
   Ν
   Mean
   Median
   Standard Deviation
   Minimum
   Maximum
   Normal
   Abnormal
    CS
    NCS
Low density lipoprotein (LDL) cholesterol (mg/dL)
   Ν
   Mean
   Median
   Standard Deviation
   Minimum
   Maximum
   Normal
   Abnormal
    CS
     NCS
High-density lipoprotein (HDL) cholesterol (mg/dL)
   Mean
   Median
   Standard Deviation
   Minimum
   Maximum
   Normal
   Abnormal
    CS
    NCS
Triglycerides (mg/dL)
   Ν
   Mean
   Median
   Standard Deviation
   Minimum
   Maximum
   Normal
   Abnormal
     CS
    NCS
Sodium (mEq/L)
   Ν
   Mean
   Median
```

Standard Deviation Minimum Maximum Normal Abnormal CS NCS Potassium (mEq/L) Ν Mean Median Standard Deviation Minimum Maximum Normal Abnormal CS NCS Calcium (mg/dL) Mean Median Standard Deviation Minimum Maximum Normal Abnormal CS NCS Phosphorus (mg/dL) Mean Median Standard Deviation Minimum Maximum Normal Abnormal CS NCS Chloride (mEq/L) Ν Mean Median Standard Deviation Minimum Maximum Normal Abnormal CS NCS B12 Vitamin (pg/) Ν Mean Median Standard Deviation Minimum Maximum Normal

```
Abnormal
    CS
     NCS
Folic acid (ng/mL)
   Mean
   Median
   Standard Deviation
   Minimum
   Maximum
   Normal
   Abnormal
    CS
    NCS
HbA1c (%)
   Ν
   Mean
   Median
   Standard Deviation
   Minimum
   Maximum
   Normal
   Abnormal
    CS
    NCS
Fasting blood insulin (\mu IU/mL))
   Ν
   Mean
   Median
   Standard Deviation
   Minimum
   Maximum
   Normal
   Abnormal
     CS
    NCS
Fasting blood glucose (mg/dL)
   Mean
   Median
   Standard Deviation
   Minimum
   Maximum
   Normal
   Abnormal
     CS
     NCS
```

CS: Clinically significant; NCS: Not clinically significant.

Table B 22 – Tests for liver function – Safety population

Table B 22 — Tests for liver function — Safety po	Total (n=xx)		
	V16	V22	V28
SGOT (U/L)			
N			

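### The glucose stopping threshold is given as 275 mg/dL (15.5 mmol/L), but 275 mg/dL is 15.3 mmol/L

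*Protocol*

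**What the plan says.** Protocol 7.5.2.1 (Changes in blood glucose) requires a patient to leave the study for symptoms of uncontrolled diabetes and/or "blood glucose levels consistently above 275 mg/dL (15.5 mmol/L), in spite of appropriate therapeutic interventions". An HbA1c of 10% or more despite treatment is a separate trigger.

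The same section gives two lower thresholds, for referral to a diabetes expert, also in both units: "fasting plasma glucose > 130 mg/dL (7.2 mmol/L" for the fasting value and "180 mg/dL (10 mmol/L) in two consecutive measurements" for the post-prandial one. The synopsis repeats these two pairs but does not give the stopping value.

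The amendment that raised the stopping limit states it in mg/dL only. Its rationale says that patients with "blood glucose values consistently above 275 mg/dL instead of 200 mg/dL must be withdrawn from the study", and its list of changes to 7.5.2.1 says "blood glucose minimum levels have been changed from 200 to 275 mg/dL".

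Protocol 6.4.5.1 lists uncontrolled diabetes mellitus among the reasons for withdrawal, without a numeric limit. Section 7.5.2.1 is therefore the only place in the body of the protocol that puts a number on the glucose stop.

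**The concern.** A threshold quoted in two units should be one threshold. The two referral thresholds imply a conversion factor of about 18 mg/dL per mmol/L; the stopping threshold implies about 17.7. If the factor of 18 is right, the stopping rule has two different limits depending on the unit read, and the mmol/L limit is the higher one.

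The rule is a mandatory safety stop, and the protocol's background sections report hyperglycemia with this drug. Section 12 allows no authorized deviations, so the rule ought to have a single value. Anyone applying the mmol/L figure would keep a patient on treatment at a level where the mg/dL figure requires discontinuation.

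**Working it through.** **Inputs**, all from Protocol 7.5.2.1:

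| Threshold | mg/dL | Stated mmol/L |
|---|---|---|
| Referral, fasting | 130 | 7.2 |
| Referral, post-prandial | 180 | 10 |
| Discontinuation | 275 | 15.5 |

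One outside constant is used: a glucose molar mass of about 180.16 g/mol, which gives mmol/L = (mg/dL) / 18.016.

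**Step 1: recalculate the stated figures.**
- 130 / 18.016 = 7.22; stated 7.2, reproduced.
- 180 / 18.016 = 9.99; stated 10, reproduced.
- 275 / 18.016 = 15.26, which rounds to 15.3; stated 15.5, not reproduced.

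**Step 2: use the protocol's own pairs, without the outside constant.** The implied factor is mg/dL divided by mmol/L.
- 130 / 7.2 = 18.06
- 180 / 10 = 18.00
- 275 / 15.5 = 17.74

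**Step 3: ask whether rounding explains the gap.** A figure given to one decimal stands for a range of plus or minus 0.05.
- 7.2 covers 7.15 to 7.25, so the factor lies between 130 / 7.25 = 17.93 and 130 / 7.15 = 18.18.
- 15.5 covers 15.45 to 15.55, so the factor lies between 275 / 15.55 = 17.68 and 275 / 15.45 = 17.80.

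The ranges do not overlap. Over the factors that the 130/7.2 pair allows, 275 mg/dL lies between 275 / 18.18 = 15.13 and 275 / 17.93 = 15.34 mmol/L, below the 15.45 needed to round to 15.5. The 180/10 pair is less decisive: if 10 is a whole number standing for 9.5 to 10.5, the factor could be anywhere from 180 / 10.5 = 17.14 to 180 / 9.5 = 18.95. The 130/7.2 pair settles the point alone.

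**Step 4: try rounded conversion factors.** Divisors of 18.0, 18.0156, 18.016, 18.018, 18.02 and 18.2, and multipliers of 0.055, 0.0555, 0.05551, 0.0556 and 0.056, give 15.11 to 15.40 mmol/L for 275 mg/dL. None gives 15.5.

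**Step 5: size of the discrepancy.**
- 15.5 × 18.016 = 279.2 mg/dL. Values that round to 15.5 mmol/L run from 15.45 × 18.016 = 278.3 to 15.55 × 18.016 = 280.1 mg/dL.
- 279.2 − 275 = 4.2 mg/dL, and 4.2 / 275 = 1.5%.
- 15.5 − 15.26 = 0.24 mmol/L.

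**The case against.** The strongest reply is that the slip has almost no consequence.

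- **Units in use.** All sites are in Brazil, the protocol puts mg/dL first in each glucose threshold, and the SAP table shells report "Fasting blood glucose (mg/dL"). The bracket is probably a convenience conversion that nobody would act on.
- **Resolution of the rule.** The criterion depends on glucose being persistently high despite treatment. It specifies no number of readings, interval or sample type. A difference of 4 mg/dL is finer than that judgment.
- **Other safeguards.** Symptoms of uncontrolled diabetes and HbA1c are independent triggers, referral to a diabetes expert is advised at much lower levels, and 6.4.5.1 lets the investigator withdraw a patient at any time.
- **Reading error.** The figure appears once and differs by one digit from the correct one, so a fault in reading the PDF is conceivable.

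The first three points stand as limits on the importance of the error, with one qualification. Protocol 10.5.3.2 and SAP 5.5.3.2 both say that all laboratory values will be converted to SI units, so the SAP shells are mixed evidence on units and someone could compare SI data with the bracketed figure. The case that 275 mg/dL was intended rests on the amendment text, not on the shells. Nothing positively suggests a misread digit. None of these points makes 15.5 mmol/L equal to 275 mg/dL.

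**Conclusion.** The concern holds. As written, 7.5.2.1 defines two stopping limits: 275 mg/dL, and a mmol/L figure equivalent to about 279 mg/dL. The mmol/L figure is the wrong one.

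This is a minor point. Only a patient persistently above 275 but not above about 279 mg/dL, without symptoms of uncontrolled diabetes and with HbA1c below 10%, would be classified differently by the two units; few patients, if any, are likely to be in that position. It is a wrong number in a safety rule, not a weakness in the rule's design.

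The conclusion assumes that the published text shows the sponsor's figure correctly. The choice of which figure to keep assumes that the amendment's mg/dL value is the decision that was made.

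**What to change.** In Protocol 7.5.2.1, change 15.5 mmol/L to 15.3 mmol/L and leave 275 mg/dL as it is. Check that any site instructions or data-review limits derived from this section carry the same pair. The cost is a one-figure correction that can go in with the next protocol change; no procedure, table or analysis needs to be altered.
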